1.2.2 Clinical Experience

No human clinical studies have been conducted with NFX-179.

1.3 Risk Benefit Assessment

Detailed information about benefits and potential risks of NFX-179 may be found in the Investigators Brochure (IB). The benefit risk ratio is considered favorable.

2 STUDY OBJECTIVES AND ENDPOINTS

The objectives of this study include:

- Primary objectives:
 - o To determine the safety and tolerability of treatment with NFX-179 Gel 0.05%, 0.15% and 0.50% when applied once daily (QD) for 28 days
 - O To determine the pharmacodynamic activity of NFX-179 Gel as defined by suppression of phospho-ERK (p-ERK) levels in defined cutaneous neurofibroma (cNF) tumors for each NFX-179 Gel group compared with the Vehicle Gel group after 28 days of QD treatment.
- Secondary objectives:
 - To determine the effect of NFX-179 Gel defined as the percent change in neurofibroma volume after 28 days of QD treatment based on tumor volume derived from ruler measurements, ultrasound and digital imaging
 - To determine the effect of NFX-179 Gel on the change from baseline in the Subject's Self-Assessment grade after 28 days of QD treatment
 - o To determine the effect of NFX-179 Gel on the change from baseline in the Physician's Tumor Assessment grade after 28 days of QD treatment.

The endpoints being evaluated include:

- Primary endpoints include:
 - Pharmacodynamic activity of NFX-179 Gel as defined by suppression of p-ERK levels in Target cNF Tumors in each NFX-179 Gel group compared with the Vehicle Gel group after 28 days of QD application
 - Safety and tolerability of treatment with NFX-179 gel (0.05%, 0.15% and 0.50%) when applied QD for 28 days
 - o Assessment of adverse events (AEs)/serious adverse events (SAEs).
- Secondary endpoints include:
 - o Percent change in cNF tumor volume after 28 days of QD application
 - Systemic exposure of NFX-179 Gel during the clinical study after 28 days of QD application
 - o Change in Subject's Self-Assessment grade after 28 days of QD application
 - Change in Physician's Tumor Assessment grade after 28 days of QD application.

3 STUDY OVERVIEW

3.1 Study Design

This study of NFX-179 is a double-blind, randomized, vehicle-controlled, parallel-group study, evaluating safety, tolerability, pharmacokinetics and pharmacodynamic activity in subjects with cutaneous neurofibromas.

At Visit 1, the investigator will identify 6 cNF tumors (Study cNF Tumors) that fulfill the enrollment criteria. The 5 Target cNF Tumors are for treatment with the assigned study

medication. One of the 5 Target cNF Tumors must be on the face, and 4 Target cNF Tumors must be on the anterior trunk or upper extremities. The 1 Untreated cNF Tumor must be on the anterior trunk or upper extremities and will not receive study medication applications. At select sites the Target cNF Tumors will be measured using high frequency ultrasound to determine volume throughout the study. The assigned study medication will be applied the Target cNF Tumors once daily (QD) during the 28-day treatment period.

At Visit 2 (Day 1) eligible subjects will be randomized and will begin the 28-day QD treatment period.

Subjects will be seen at Visits 3 and 4 (Days 8 and 15) for follow-up visits during the treatment period. At Visit 5 (Day 29) subjects will be seen for the last treatment period visit, will have the 5 Target cNF Tumors and the 1 Untreated cNF Tumor excised 4 (±1) hours after the last study medication application, and will start a 28-day no treatment follow-up period. Subjects will be seen at Visit 6 (Day 36-50) for follow-up care of the Visit 5 excision wounds. Subjects will be seen for Visit 7 (Day 57) for an end of study visit.

No topical treatments other than the study medication will be applied to any of the Study cNF Tumors for the duration of the study.

3.2 Scientific Rationale for Study Design

NFX-179 is formulated as a gel for topical administration. Since application of a gel can be expected to have an effect on the treated cNF tumors, use of a vehicle gel is deemed necessary in this study to differentiate any effects due to the vehicle from the active substance. Use of a vehicle also allows to control any effect that participation in the clinical study may introduce as a result of a more careful or otherwise different management of the cNF. Finally, use of a vehicle controls bias in those safety and efficacy assessments that rely on subjective judgement by the subject or the investigator.

Systemic absorption of NFX-179 following single topical application to the 5 Target cNF Tumors is expected to be extremely low, based on serum values observed in animal studies presented in the IB. However, to confirm that systemic exposure of NFX-179 is low in human

subjects as well, blood samples will be taken to assess NFX-179 serum levels throughout the study.

3.3 Dose Selection Rationale

The selection of dose, dosing interval and duration has taken into account the results of the nonclinical pharmacology, PK and toxicology studies, which are presented in the IB. The QD topical application frequency at the proposed concentrations is expected to result in continuous exposure at efficacious levels in a safe range. Further details on the dose selection rationale are provided in the NFX-179 IB.

3.4 End of Study Definition

The end of the study is defined as the date of the last visit of the last subject in the study globally.

If NFlection, Medical Monitor or designee, monitor, or appropriate regulatory officials indicate that the study should be halted or that a study site should be terminated, this action may be taken after appropriate consultation between NFlection and the appropriate parties. NFlection has the right to terminate this study at any time for any reason. Conditions that may warrant termination of the study include, but are not limited to, the following:

- The discovery of an unexpected, serious, or unacceptable risk to the subjects enrolled in the study.
- A decision by NFlection to suspend or discontinue testing, evaluation, or development of the product.

3.5 Study Duration

The duration of study participation for each subject is anticipated to be a maximum of 88 days. Including a 28-day screening period, a 28-day treatment period and a 28-day notreatment follow-up period. The last study visit has a window of ± 4 days.

The planned duration of the study from first subject first visit to last subject last visit is planned to be approximately 64 weeks. The study end date is the date of the last subject's last visit.

4 STUDY POPULATION

This study will enroll male and female subjects aged 18 years and older, with a clinical diagnosis of NF1.

4.1 Number of subjects

Approximately 56 subjects will be randomized to 1 of the 4 study medication treatment groups at approximately 6 United States (US) investigational centers with the goal of at least 48 subjects completing the study.

4.2 Study Entry Criteria

4.2.1 Inclusion Criteria

In order to be eligible to participate in this study, the subject must fulfill all the following criteria:

- 1. Subject is at least 18 years of age
- 2. Subject must provide written informed consent prior to any study procedures
- 3. Subject must have a clinical diagnosis of NF1
- 4. Subject has 6 Study cNF Tumors (5 Target cNF Tumors [1 on the face; 4 on the anterior trunk or upper extremities] that will be treated with the assigned study medication; 1 Untreated cNF Tumor on the anterior trunk or upper extremities) that each meet the following criteria:
 - Has, in the investigator's opinion, a clinically typical appearance
 - Is dome shaped
 - Is not pedunculated
 - Is a discrete tumor
 - Is not irritated
 - Is not in an area subject to repeated trauma (e.g., area that is shaved, on the beltline, under a bra strap, etc.)
 - Does not have an active cutaneous infection
 - Has a diameter that is ≥ 5 mm and ≤ 10 mm
 - Has a height of ≥2mm
 - Is, when centered in the center of the provided template, the only cNF tumor visible
 - Is not within 5mm of the orbital rim.
- 5. Subject is willing to have the 5 Target cNF Tumors and the 1 Untreated cNF Tumor excised at the end of the treatment period
- 6. Subject is willing to have hair in the area surrounding the Target cNF Tumors shaved, if necessary, to obtain photographs
- 7. Subject is willing to minimize exposure of each Target cNF to natural and artificial ultraviolet radiation

- 8. Subject is willing to forego treatment of the Target cNF Tumors, except protocol specified therapy, during the study
- 9. Female subjects who are women of childbearing potential must have a negative urine pregnancy test result and be willing to use a protocol approved, contraceptive method for the duration of the study
- 10. Subject is willing and able to follow all study instructions and to attend all study visits.

No waivers to the inclusion criteria are permitted.

4.2.2 Exclusion Criteria

A subject who meets any of the following criteria will be excluded from participation in this study:

- 1. Subject has applied any of the following topical products in the previous 30 days on or in proximity to any Study cNF Tumor that, in the investigator's opinion, impairs evaluation of any the tumor or which exposes the subject to an unacceptable risk by study participation:
 - Corticosteroids
 - Retinoids (e.g., tazarotene, tretinoin, adapalene)
 - > 5% of an alpha-hydroxy acid (e.g., glycolic acid, lactic acid)
 - Fluorouracil
 - Imiquimod
- 2. Any Study cNF Tumor has ever been treated with an MEK inhibitor or a BRAF inhibitor
- 3. The subject has used any of the following systemic medications in the noted time period:
 - Retinoids (e.g., etretinate, isotretinoin) within the previous 90 days
 - MEK inhibitors within the previous 180 days
 - BRAF inhibitors within the previous 180 days
- 4. Subject has a history of hypersensitivity to any of the ingredients in the study medications
- 5. Subject has any known intercurrent illness or physical condition that would, in the investigator's opinion, impair evaluation of a Target cNF Tumor or which exposes the subject to an unacceptable risk by study participation
- 6. Subject has, in the investigator's opinion, clinically relevant history of liver disease, including viral hepatitis, current alcohol abuse, or cirrhosis
- 7. Subject has a history of metastatic disease, or active cancer (excluding non-melanoma skin cancer, Stage I cervical cancer, ductal carcinoma *in situ* of the breast, or Stage 0 chronic lymphocytic lymphoma) within the previous 5 years
- 8. Subject has any condition (e.g., other skin conditions or diseases, metabolic dysfunction, physical examination findings, clinical laboratory findings) or situation (e.g., vacation, scheduled surgery) that would, in the investigator's opinion, impair evaluation of a Target cNF Tumor or which exposes the subject to an unacceptable risk by study participation

9. Subject has participated in an investigational drug trial in which administration of an investigational study medication occurred within the previous 30 days.

No waivers to the exclusion criteria are permitted.

4.3 Subject identifier (SI)

At Visit 1 (Screening) the investigator or designee will assign a unique four-digit subject identifier (SI) to each subject.

The SI format will be NN-NN where the first 2 digits are the investigational center site number (using leading zeroes as appropriate) assigned by NFlection. The final 2 digits are the subject number and must be assigned in ascending numerical order, without omitting or repeating any number, starting with 01 at each investigational center. For example, the SI for the second subject that signs an informed consent at site number 04 would be 04-02.

The subject will be identified using the SI in all study documentation for the duration of the study.

4.4 Screen Failures

A subject who consents to participate in the study but is not subsequently randomized to study medication will be considered a screen failure.

A minimal set of screening failure information is required to ensure appropriate reporting of screen failure subjects and to respond to queries from regulatory authorities. For detailed screening failure requirements please refer to the case report form (CRF) completion guidelines.

Individuals whose screening data do not meet the criteria for participation in this study (*i.e.*, screen failure) may be rescreened after consultation of the Medical Monitor. If the subject will be rescreened, a new SI will be created.

4.5 Early Termination Visit

The investigator should complete the following study procedures for subjects who prematurely discontinue from the study:

- For subjects who are randomized and discontinue from the study prior to Visit 5 complete the Visit 5 procedures except Study Tumor excision
- For subjects who complete Visit 5 and discontinue from the study prior to Visit 6 complete the Visit 6 procedures
- For subjects who complete Visit 6 and discontinue from the study prior to Visit 7 complete the Visit 7 procedures.

Detailed instructions for documenting subjects who prematurely discontinue from the study will be included in the CRF guidelines.

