4.8 Subject discontinuation from the study

Subjects will be informed that they are free to withdraw from the study at any time and for any reason.

The investigator may remove a subject from the study if, in the investigator's opinion, it is not in the best interest of the subject to continue the study. The investigator must remove a subject from the study if the subject experiences:

- A Serious Adverse Event the investigator defines as related to the study medication, regardless of the intensity of the event
- A non-serious adverse event the investigator defines as related to study medication that has a severity of severe and requires treatment to resolve.

Examples of other reasons subjects may be discontinued from the study are a change in compliance with an inclusion or exclusion criterion, occurrence of AEs, occurrence of pregnancy or use of a prohibited therapy. Notification of discontinuation will immediately (within 24 hours) be made to the NFlection study monitor.

All withdrawn subjects with ongoing AEs will be followed as appropriate.

The study may be discontinued at the discretion of NFlection. Some examples of reasons for

discontinuation are the occurrence of the following:

- Increased frequency, severity or duration of known AEs
- Medical, regulatory or ethical reasons affecting the continued performance of the study
- Difficulties in the recruitment of subjects.

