4.12.8 Study medication application

The study medications are for external, topical use on each Target cNF Tumor only and on the appropriate study subject only.

To perform a study medication application the subject should:

- Wash her/his hands before starting the application
- Avoid applying the study medication any open wounds or obviously infected skin
- Apply an amount of the assigned study medication sufficient to cover each Target cNF with a thin layer of the medication
- Gently rub in the study medication until no visible accumulation is evident
- Wash her/his hands after completing the application

The subject must apply study medication to the entire area of each Target cNF Tumor limiting exposure to the un-affected skin surrounding the tumor.

At Visit 2, an investigational center staff member will instruct the subject on the proper application technique. The staff member will observe the subject's study medication application to ensure proper application technique and record the time the subject completes the application to the last Target cNF Tumor as the Application Completion Time. The staff member will monitor the subject for adverse events for at least 20 minutes after the Application Completion Time. The subjects are to continue QD application of the assigned study medication to each Target cNF Tumor for 4 weeks with 24 (±6) hours between applications.

At Visit 5, the study medication application will be performed by the subject as part of the visit procedures at the investigational center. Record the time the subject completes the application to the last Target cNF Tumor as the Application Completion Time. The study medication tubes will be collected after the application at this visit.

For Visits 3 and 4 subjects should not apply the study medication within 18 hours prior to the study visit.

Prior to Visit 5 subjects must be instructed to perform the study medication application 24 (±6) hours prior to the visit.

After completing a study medication application, a subject should not:

- Wash or submerse any Target cNF Tumor for at least 6 hours
- Apply any topical products (*e.g.*, cosmetics, emollient/moisturizer, sunscreens) to any Target cNF Tumor for at least 6 hours.

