5.2.4 Visit 5/Day 29 (End of Treatment; start of no treatment follow-up)

This visit must occur 28 days (± 4 days) after Visit 2.

At selects sites performing PK sample collection at this visit:

- Subjects will be confined at the investigational center for approximately 6 hours for the collection of PK blood samples and for excision of the 6 Study cNF Tumors
- This visit must be scheduled so that the previous study medication application was completed 24 (±6) hours prior to the 0-hour PK blood sample.

At sites NOT performing PK sample collection at this visit: subjects will be confined at the investigational center for approximately 6 hours for excision of the 6 Study cNF Tumors.

At this visit, the investigator or designee will perform the following procedures:

- 1. Query the subject in a non-directive manner about any changes in her/his health since the previous visit and report all AEs as appropriate
- 2. Query the subject about any changes in her/his concomitant therapies since the previous visit and report changes as appropriate
- 3. Confirm the subject has followed all study instructions including, at select sites, appropriate timing of the previous study medication application for PK blood sampling
- 4. Measure vital signs
- 5. Perform a urine pregnancy test for WOCBP
- 6. Confirm the location of the 6 Study cNF Tumors (5 Target cNF Tumors and 1 Untreated cNF Tumor)
- 7. Measure the dimensions of each Target cNF Tumor
- 8. Have the subject perform an SSA for each Target cNF Tumor
- 9. Have the subject perform an LTA of the symptoms for each Target cNF Tumor
- 10. Perform a PTA for each Target cNF Tumor
- 11. The investigator will perform an LTA of the signs for each Target cNF Tumor
- 12. At select sites: Perform an ultrasound of each Target cNF Tumor
- 13. Take standardized color photographs of each Target cNF Tumor
- 14. Perform an ECG
- 15. Collect samples for clinical laboratory tests then conduct the appropriate activities as indicated below.

At select sites performing PK sample collection at this visit:

- 16. Collect 0-hour blood sample for PK analysis 24 (±6) hours after the previous study medication application and prior to the Visit 5 study medication application
- 17. Have the subject perform the last study medication application and record the Application Completion Time
- 18. Have the subject perform a post-application LTA of the symptoms for each Target cNF Tumor 10 (±4) minutes after the Application Completion Time

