- 19. The investigator will perform a post-application LTA of the signs for each Target cNF Tumor 20 (±4) minutes after the Application Completion Time
- 20. Collect post-application blood samples for PK analysis
- 21. 4 (±1) hours after the Application Completion Time excise the 6 Study cNF Tumors (5 Target cNF Tumors and 1 Untreated cNF Tumor)
- 22. Collect and weigh study medication
- 23. Review the study instructions with the subject
- 24. Schedule Visit 6.

At sites NOT performing PK sample collection at this visit:

- 16. Have the subject perform the last study medication application
- 17. Have the subject perform a post-application LTA of the symptoms for each Target cNF Tumor 10 (±4) minutes after the Application Completion Time
- 18. The investigator will perform a post-application LTA of the signs for each Target cNF Tumor 20 (±4) minutes after the Application Completion Time
- 19. 4 (±1) hours after the Application Completion Time excise the 6 Study cNF Tumors (5 Target cNF Tumors and 1 Untreated cNF Tumor)

Date: 24-JUL-2020 Page 42 of 78 Supersedes: NEW

- 20. Collect and weigh study medication
- 21. Review the study instructions with the subject
- 22. Schedule Visit 6.

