5.2.6 Visit 7/Day 57 (End of study, early termination)

This visit must occur 56 days (± 4 days) after Visit 2 and 7 (± 4) days after Visit 6.

At this visit, the investigator or designee will perform the following procedures:

- 1. Query the subject in a non-directive manner about any changes in her/his health since the previous visit and report all AEs as appropriate
- 2. Query the subject about any changes in her/his concomitant therapies since the previous visit and report changes as appropriate
- 3. Confirm the subject has followed all study instructions
- 4. Measure vital signs
- 5. Discharge the subject from the study.

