6.1.7 Urine pregnancy tests

At Visits 1, 2 (prior to randomization) and 5, the investigator or designee will perform a urine pregnancy test for subjects who are WOCBP. The urine pregnancy test kits used must have a minimum sensitivity of 25-mIU β-HCG/milliliter (mL) of urine.

Subjects who are WOCBP must have a negative pregnancy test result at the Visit 1 to be enrolled in the study and at Visit 2 to be randomized.

If the result of any post-treatment urine pregnancy test is positive, the subject will be withdrawn from the study and the subject's pregnancy documented and followed.

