7.6.2 Protocol approved methods of birth control

The investigator will discuss the potential risk factors associated with pregnancy and the importance of maintaining a highly effective method of birth control with all WOCBP. All WOCBP must use a protocol approved method of birth control throughout the duration of the study and for 30 days after the last study medication application.

For this study protocol approved methods of birth control include:

- Women who are abstinent from reproductive sex as a matter of lifestyle (*i.e.*, women having sex with women); or who are abstinent are acceptable methods of contraception (as these methods, if followed consistently, are at least as effective as hormonal birth control pills)
- Combined (estrogen and progestogen containing) hormonal contraception associated with inhibition of ovulation:
 - o Oral
 - Transdermal
 - Intravaginal
- Progestogen-only hormonal contraception associated with inhibition of ovulation:
 - o Oral
 - o Implantable
 - o Injectable
- Intrauterine device (IUD)
- Intrauterine hormone-releasing system

WOCBP must be on at least 1 protocol approved method of birth control for the following time periods prior to Visit 1:

- Abstinence (≥30 days)
- Implants (on a stable dose for ≥ 30 days)
- Injectables (on a stable dose for \geq 30 days)
- Patches (on a stable dose for ≥ 30 days)
- Combined oral contraceptives (on a stable dose for \geq 30 days)
- Intrauterine devices (inserted for ≥ 30 days).

Prior to trial enrollment the investigator must discuss with all WOCBP the potential risk factors associated with a pregnancy during the study and the importance of avoiding pregnancy during study participation. The subject must sign an informed consent form documenting this discussion. During the trial, all WOCBP will be instructed to contact the investigator immediately if they suspect they might be pregnant (*e.g.*, missed or late menstrual period). If a subject or investigator suspects that the subject may be pregnant prior to study medication administration, the study medication must be withheld until the results of a pregnancy test are available. If pregnancy is confirmed, the subject must not receive study medication and must be discharged from the study.

If, following the first study medication application it is determined that the subject may have been or was pregnant at the time of study medication exposure (including 30 days after the last

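### Section 4.5 carries the Visit 5 study medication application into the early-termination visit and does not say whether it applies to subjects removed for safety reasons

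*Combined protocol and SAP*

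**What the plan says.** All references are to the combined protocol.

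- **Section 4.5** has three stages. For subjects who discontinue after randomization and before Visit 5, the instruction is to "complete the Visit 5 procedures except Study Tumor excision". No other step is exempted and no withdrawal reason is treated separately.
- **Section 4.12.8** makes dosing part of that visit: "At Visit 5, the study medication application will be performed by the subject as part of the visit procedures at the investigational center".
- **Section 5.2.4** repeats this in both step lists. Step 17 at PK sites is "Have the subject perform the last study medication application and record the Application Completion Time", and step 16 at the other sites is "Have the subject perform the last study medication application". Symptom and sign assessments follow at about 10 and 20 minutes. Section 6.3.2 adds PK samples at 30 minutes and at 1, 2 and 4 hours at select sites.
- **Section 4.8** makes removal compulsory for "A Serious Adverse Event the investigator defines as related to the study medication, regardless of the intensity of the event", and for a related non-serious event that is severe and needs treatment.
- **Section 4.12.9** makes removal compulsory when daily application to all target tumors cannot be performed for more than 4 days in a row.
- **Section 6.1.7** covers a positive pregnancy test: "If the result of any post-treatment urine pregnancy test is positive, the subject will be withdrawn from the study".
- **Section 7.6.2** adds: "If pregnancy is confirmed, the subject must not receive study medication and must be discharged from the study". It later waives discontinuation procedures that pregnancy contraindicates.

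**The concern.** The subjects most likely to reach a pre-Visit 5 termination visit for safety reasons are those whom Sections 4.8 and 4.12.9 require the investigator to take off the study because of the product. Section 4.5 then sends them through a procedure list that contains another application of it.

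No human study of NFX-179 had been done before this one (Section 1.2.2), and safety and tolerability are a primary objective (Section 2). What a site does at the termination visit therefore matters both to the subject and to the tolerability record. As written, two sites could read Section 4.5 differently, one including the application and one leaving it out, and each could say that it followed the protocol.

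**Working it through.** No alpha, power, rate or sample size enters this point. The check is to apply the Section 4.5 instruction to the Section 5.2.4 lists and compare what is left with the removal rules.

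**Step 1: remove only what Section 4.5 removes.**

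| Site type | Steps listed | Excision step | Steps left | Application | Post-application assessments | Post-application PK |
|---|---|---|---|---|---|---|
| PK sites | 24 | 21 | 24 − 1 = 23 | step 17 | steps 18, 19 | step 20 (4 samples) |
| Other sites | 22 | 19 | 22 − 1 = 21 | step 16 | steps 17, 18 | none |

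The application and everything timed from it stay in, apart from the excision.

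**Step 2: compare with each removal rule.**

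- *Related serious event, or related severe event needing treatment (4.8).* Removal is compulsory. Section 4.8 does not say in words that no further application may be made, so the conflict is with the evident purpose of the rule, not with a stated prohibition.
- *Inability to continue daily application (4.12.9).* The same reasoning applies. There is also a timing problem at PK sites. Step 16 asks for the 0-hour sample 24 (±6) hours after the previous application, so at most 24 + 6 = 30 hours. If such a subject has applied nothing for more than 4 days, the interval exceeds 4 × 24 = 96 hours, and the step cannot be done as specified.
- *Pregnancy (6.1.7, 7.6.2).* Here there is an explicit bar on dosing and a waiver for contraindicated procedures. Section 4.5 points to neither. In the Visit 5 list the pregnancy test is step 5 and the application is step 16 or 17, with no condition in the list joining them.

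**Step 3: look for text that resolves it.** The CRF guidelines mentioned in Section 4.5 are described as covering documentation of early discontinuations. Section 4.6, on unscheduled visits, leaves additional procedures to the investigator's opinion of what is appropriate. Section 4.5 has no such wording. No general exemption of the application step was found.

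**The case against.** The best defense is that no reasonable site would dose a subject just removed for a drug-related event. Section 4.5 uses should, Section 7 makes the investigator responsible for appropriate medical care, and Section 11.4 allows deviation to eliminate an immediate hazard. The Visit 5 application is also timed to the excision 4 (±1) hours later and, at select sites, to PK sampling. Without excision, a non-PK site has little reason to carry it out. These points reduce the practical risk and make literal compliance the worst case. They do not supply the missing instruction, and outside an immediate hazard Section 11.4 asks for prior sponsor and IRB/EC approval before deviating.

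The defense on pregnancy is stronger. The specific rules in Section 7.6.2 can fairly be read as limiting the general one in Section 4.5. The bar on dosing does follow text about suspected pregnancy before medication is given, so a narrower reading is possible. What remains is mainly a missing cross-reference.

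Three stronger readings are tempting, and the documents do not support them:

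- **A competing early-termination visit.** The heading of Section 5.2.6 attaches early termination to Visit 7, which has no application. This fits the third stage of Section 4.5, which sends subjects who leave between Visits 6 and 7 to the Visit 7 procedures. There is no conflict.
- **Eight affected subjects.** Sections 4.1 and 4.9 imply 56 − 48 = 8 non-completers (8/56 = 14%). That allowance covers all non-completion through Visit 7, including departures after Visit 5 and subjects lost to follow-up who attend no visit. The Synopsis and Section 8.1 also give about 48 randomized instead of 56.
- **Contaminated Visit 5 summaries.** Nothing assigns early-termination tolerability or PK values to the Visit 5 summaries. The Synopsis confines LOCF to efficacy data, and Section 8.3.1 leaves details to a SAP still to be written.

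**Conclusion.** The point holds as a wording defect with a safety consequence. Followed as written, Section 4.5 calls for a further application after compulsory removal for a related serious event, a related severe event needing treatment, or inability to continue daily application. The contradiction is by implication for Sections 4.8 and 4.12.9. For pregnancy it is explicit between Section 4.5 and the bar in Section 7.6.2, but largely answered within Section 7.6.2 itself.

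In procedural terms, each affected subject would have one application to 5 tumors, two post-application assessments and, at PK sites, four post-application samples. The number of such subjects cannot be derived: the documents give no rate for withdrawals before Visit 5, or for safety withdrawals among them. Alpha, power and sample size are not affected.

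The conclusion assumes that the Section 4.5 exception is exhaustive, as its wording indicates, and that no operational document outside those supplied removes the application step.

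**What to change.** Reconcile Sections 4.5 and 5.2.4 with Sections 4.8, 4.12.9, 6.1.7 and 7.6.2:

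1. In the first stage of Section 4.5, replace the blanket reference with an explicit list of the Visit 5 steps that apply at a pre-Visit 5 termination visit.
2. For each withdrawal reason, state whether the application, the post-application tolerability assessments and the PK steps apply. The sponsor decides the clinical rule; the text must only say what it is.
3. Cross-refer to the pregnancy provisions of Sections 6.1.7 and 7.6.2.
4. Record the time since the last application at that visit, so that any tolerability or PK value collected there can be interpreted.

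Keep the three-stage structure of Section 4.5. The cost is a few lines of protocol text and one CRF field, with no added visits, subjects or staff.
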